## 8.2 Interim Data Review

Interim reports with statistical analyses will be prepared twice per year until the initial treatment results have been presented or published. In general, the interim reports will contain the following information:

- Patient accrual rate with a projected completion date (while the study is still accruing)
- Total patients accrued
- Frequencies and severity of adverse events
- Compliance rates of treatment delivery

## 9.0 ASSESSMENT OF EFFICACY

### 9.1 Efficacy Parameters

Tumor response will be assessed using the RECIST criteria.

For tumors targeted by radiation:

- Complete Response (CR): Disappearance of all target lesions
- Partial Response (PR): At least a 30% decrease in the sum of the LD of target lesions, taking as reference the baseline sum LD
- Stable Disease (SD): Neither sufficient shrinkage to qualify for PR nor sufficient increase to qualify for PD, taking as reference the smallest sum LD since the treatment started
- Progressive Disease (PD): At least a 20% increase in the sum of the LD of target lesions, taking as reference the smallest sum LD recorded since the treatment started or the appearance of one or more new lesions

Patients with a global deterioration of health status requiring discontinuation of treatment without objective evidence of disease progression at that time should be classified as having "symptomatic deterioration". Every effort will be made to document the objective progression even after discontinuation of treatment.

### 9.2 Method and Timing

Tumors will be measured on axial CT chest images. The radiation treatment planning scan will be used as baseline. The 3-months post-treatment scan will be used for comparison.

### 9.3 Toxicity Profile

Toxicity will be measured by the Common Terminology Criteria for Adverse Events (CTCAE) version 4.0.

## 10.0 STATISTICAL CONSIDERATIONS

The primary objective of this protocol is to provide a preliminary evaluation of the safety and efficacy of re-irradiation with proton beam radiotherapy in patients with recurrent thoracic cancer. Ideally this therapy should have a grade 3 toxicity rate of < 25% and a local control rate of > 80%.

Twenty patients will be enrolled. If 7 or more of the 20 patients experience grade 3 toxicity, then we would be at least 80% confident that the true toxicity rate exceeds 25%; conversely, if 3 or fewer of the 20 patients experience grade 3 toxicity, then we would be at least 80% confident that the true toxicity rate is less than 25%. An intermediate result, 4-6 patients with grade 3 toxicity, would be regarded as inconclusive.

With regard to efficacy, if the therapy results in 14 or fewer of the 20 patients with local tumor control, then we would be at least 80% confident that the true local control rate is less than 80%; conversely, if 18 or more of the patients have local tumor control, then we would be at least 80% confident that the true local control rate exceeds 80%. An intermediate result, 15-17 patients with local tumor control, would be regarded as inconclusive.

An early stopping rule will be imposed for grade 5 adverse events, and the protocol will stop should any patients experience a grade 5 AE as described in Section 8.1. If the true rate of grade 5 AE is 10%, then there is an 88% chance that this stopping rule will be triggered.

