**Table 1. Summary of Recurrent Thoracic Radiation**

Study	Institution	# of patients	Radiation Technique	Toxicity	Local Control
Kelly et al. IJROBP 2010[8]	MD Anderson	36	SBRT (10 Gy x4 fractions or 10 Gy x5)	33% grade 3. No grade 4 or 5.	92% at 2 years
Trakul et al. JTO 2012[9]	Stanford	17	SBRT (dose fractionation varies)	13% grade 3. No grade 4 or 5.	65.5% at 1 year
Seung et al. J Cancer Therapy 2011[10]	Oregon Clinic	8	SBRT (8-20 Gy x3-5 fractions)	100% grade 2 pneumonitis. No grade 3 or higher.	86% at 1.5 years

In addition to recurrent lung cancers, other malignancies can also result in the need for repeat irradiation of the chest. For example, recurrent thymomas that were previously treated with radiation therapy can still have a relatively long disease course. In unresectable localized recurrences that show no evidence of dissemination, in patients with good performance status and life expectancy, it would be reasonable to consider repeat radiation. Patients with one thoracic cancer can also develop a second primary malignancy in the chest (i.e. esophageal cancer that was treated with radiation years ago, now with lung cancer; or breast cancer treated previously, now with lung cancer). Since radiation planning is guided by normal organ dose limits, this patient population would follow similar radiation guidelines as recurrent lung cancer patients, in terms of normal organ radiation constraints.

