### 4.2 Endpoints

#### 4.2.1 Primary Endpoint

Grade 3 or greater toxicity attributable to radiation treatment.

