## 7.0 TREATMENT PLAN

All patients will receive radiation treatment per standard of care, adhering to the normal organ radiation dose constraints outlined in this protocol. The only additional procedure related to this protocol is informed consent at enrollment.

The standard treatment outline for patients receiving radiation treatment, which also applies to patients on this protocol, begins with an initial consultation, including history and physical. Patients' prior radiation records will be obtained and reviewed. If patients are eligible and consent to repeat irradiation, they are scheduled for a radiation simulation scan, to be used for radiation treatment planning. Physicians will delineate the target tumor volume as well as normal organs to be protected in the region. A radiation plan will be generated that meets the normal organ dose limits outlined in this protocol. The plan undergoes quality assurance checks, and patients then start treatment. During treatment, patients are seen at least once weekly by the physician to assess for toxicity. After completion of radiation, patients are seen typically 3 months post-treatment with CT chest to assess for treatment response and toxicity. Additional imaging or follow up visits may take place per routine medical standard of care. Research staff will review clinical record at 3 months post-treatment. See Table 1 below for summary.

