### 7.1.6 Radiation Toxicity

Toxicity will be graded based on CTCAE 4.0. Grade two and above adverse events will be recorded in a Redcap database. The AE's will be followed for three months post-treatment.

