## 8.1 Early Stopping Rules

In the event of a grade 5 event occurring within  $\leq 30$  days after the end of treatment, there will be a temporary cessation in patient enrollment for event review. If the event is defined as possibly, probably, or definitely related to treatment (per CTCAE, v.4.0), early stopping of this trial will occur permanently. All Grade 3 and 4 AE's will be immediately monitored and reviewed by PI.

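### Section 8.1 states no action for a treatment-related death on days 31 to 90, although adverse events are followed for three months

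*Combined protocol and SAP*

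**What the plan says.** **The rule.** Section 8.1 of the combined protocol and SAP contains the only stopping rule. For a grade 5 event up to 30 "days after the end of treatment, there will be a temporary cessation in patient enrollment for event review". If the event is judged at least possibly related to treatment, the trial closes permanently. The section then adds: "All Grade 3 and 4 AE's will be immediately monitored and reviewed by PI". That sentence has no day limit and does not name grade 5.

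**The follow-up.** Section 7.1.6 says: "The AE's will be followed for three months post-treatment". The primary endpoint in Section 4.2.1 is "Grade 3 or greater toxicity attributable to radiation treatment", so a related death on day 60 counts towards it.

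**What else could bring a late death to attention.** Section 8.0 gives the PI general oversight, including of adverse-event reporting. Section 7.0 says: "Research staff will review clinical record at 3 months post-treatment". Section 8.2 says: "Interim reports with statistical analyses will be prepared twice per year until the initial treatment results have been presented or published". Those reports list the frequency and severity of adverse events, but no threshold or action is attached.

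**The stated performance.** Section 10 refers to Section 8.1 for the definition of the stopping event and then says: "If the true rate of grade 5 AE is 10%, then there is an 88% chance that this stopping rule will be triggered".

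**The concern.** Safety is the primary objective, and the trial intends to watch each patient for three months after treatment. The response to a death covers only the first 30 days of that period. Followed as written, Section 8.1 asks for less after a related death on day 45 than after a grade 3 event on the same day: the grade 3 event goes to the PI at once, and for the death no step is stated.

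At stake is whether enrolment continues after a late fatal toxicity without anyone being required to review the event promptly and record why it is acceptable to go on. The plan gives no reason for leaving the later two months without a stated response.

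**Working it through.** **1. Section 10's own figure.** With 20 patients (Section 10), a stop on one qualifying event and a 10% rate, the chance of a trigger is 1 − 0.9^20 = 1 − 0.1216 = 0.878. The stated 88% is reproduced. It applies to events that meet Section 8.1, that is, related deaths by day 30.

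**2. What is required, by event and day.**

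| Event | Up to day 30 | Days 31 to 90 |
|---|---|---|
| Grade 3 or 4 | Immediate PI review | Immediate PI review |
| Related grade 5 | Pause, review, permanent stop | No event-specific step stated |

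This gap needs no assumption. It follows from reading Section 8.1 against Section 7.1.6.

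**3. Illustrative size.** The documents give neither the rate of related death over three months (g) nor the share of those deaths falling after day 30 (s). Both are assumed here. Write e = g(1 − s) for the rate by day 30. In 20 patients:

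- chance that Section 8.1 fires = 1 − (1 − e)^20
- chance of at least one related death = 1 − (1 − g)^20
- chance of a related late death with no trigger = (1 − e)^20 − (1 − g)^20

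For g = 2% and s = 50%, e = 1%, and the last line is 0.99^20 − 0.98^20 = 0.818 − 0.668 = 15.0%.

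| g | Any related death | 8.1 fires (s = 25 / 50 / 75%) | Late death, no trigger (s = 25 / 50 / 75%) |
|---|---|---|---|
| 2% | 33.2% | 26.1 / 18.2 / 9.5% | 7.2 / 15.0 / 23.7% |
| 5% | 64.2% | 53.4 / 39.7 / 22.2% | 10.7 / 24.4 / 41.9% |
| 10% | 87.8% | 79.0 / 64.2 / 39.7% | 8.9 / 23.7 / 48.1% |

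**4. Which row to use.** Table 1 of the protocol reports no grade 5 event in its three series; the largest, for example, has "33% grade 3. No grade 4 or 5". Together they have 36 + 17 + 8 = 61 patients. The exact one-sided 95% upper limit for 0 of 61 is 1 − 0.05^(1/61) = 4.8%. The 5% and 10% rows lie above that limit, so the 2% row is the fairest guide. Table 1 covers photon SBRT series and is an imperfect comparison.

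**5. Cost of reviewing late deaths.** Suppose 1% of patients die of their cancer on days 31 to 90 and the death is judged possibly related. An added pause rule would then give an unneeded pause in 1 − 0.99^20 = 18.2% of trials. At 2% it is 1 − 0.98^20 = 33.2%. Both rates are assumptions.

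**The case against.** **The 88% is tied to the rule.** A reader might infer that Section 10 overstates the rule's sensitivity and should carry a lower figure, such as the 64.2% that follows if 10% is the three-month rate and half the deaths are late. The documents do not support this. Section 10 points to Section 8.1 for the stopping event, the next sentence gives the chance that this rule fires, and the arithmetic is right for such events. A replacement figure would put an unsourced timing assumption into the protocol. This objection stands in full.

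**A late death would not go unseen.** A reader might infer that a death on day 45 escapes all review. It does not. General oversight, adverse-event recording, the three-month record review and the twice-yearly reports all apply, and a fatal toxicity first recorded at grade 3 or 4 would already be with the PI. This also stands. What is missing is a review triggered by the death itself, together with a pause and a recorded decision.

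**A 30-day limit is defensible.** The rule closes the trial on a single possibly related death. Any cut-off produces a contrast between one day and the next. Attribution also becomes harder with time, because Section 5.1 admits all stages and allows concurrent and later chemotherapy and later surgery. That supports keeping the permanent stop at day 30. It does not explain why nothing lighter applies afterwards.

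**The size is soft.** The share of late deaths alone moves the 2% case from 7.2% to 23.7%, and the higher rates exceed the Table 1 limit. One might also count the patients enrolled after a late death as patients the fix would protect. That would overstate the benefit: in trials with an early related death as well, the existing rule also fires, and a pause may end with enrolment resuming.

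**Conclusion.** The gap is real and narrow. For a related death on days 31 to 90 no section requires an event-triggered review, a pause or a recorded decision, although the event lies within adverse-event follow-up and counts towards the primary endpoint. Read literally, Section 8.1 demands less for it than for a grade 3 event.

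As an illustration, at a 2% three-month rate of related death, 15.0% of trials would have such a death with no Section 8.1 trigger (7.2% to 23.7% for 25% to 75% of deaths late). The rate and the timing are both assumed; the existence of the gap is not.

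The primary analysis is not affected. A late related death is counted as grade 3 or greater toxicity, and the reading that 3 or fewer events in 20 support a rate below 25% stays valid with that death in the count. This is a cheap improvement to safety oversight and not a flaw in the trial's result.

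**What to change.** Keep the day-30 permanent stop and the 25% decision rule. Add to Section 8.1:

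> A grade 5 event after day 30 and within three months after the end of treatment will be reviewed by the PI immediately when it becomes known. If it is possibly, probably or definitely related to treatment, enrollment will be paused until the review is complete and the decision to continue, amend or stop is recorded and reported to the IRB.

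Section 10 needs no new figure. At most, insert the words *treatment-related* and *within 30 days after treatment* beside the 10% rate, for clarity.

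**Cost.** Two sentences and no new visit. Adverse events of grade 2 and above are already recorded for three months, and events of grade 3 or greater already need attribution for the primary endpoint. The new work is a prompt relatedness review of each late death. The follow-up visit may fall between 2 and 6 months (Table 2 footnote), so some deaths may first come to light at the record review; the wording allows for that by starting from when the event becomes known. The main downside is the unneeded pauses sized above, about 18% to 33% of trials under the assumed 1% to 2% of patients. These are pauses and not closures.

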## 11.0 DATA MANAGEMENT/CONFIDENTIALITY

The investigator will ensure that data collected conform to all established guidelines. Each subject is assigned a unique patient number to assure subject confidentiality. Subjects will not be referred to by this number, by name, or by any other individual identifier in any publication or external presentation. The licensed medical records department, affiliated with the institution where the subject receives medical care, maintains all original inpatient and outpatient chart documents.

Subject research files are stored in a secure place (or database). Access is restricted to authorized personnel.

